3. STUDY DESIGN OVERVIEW

Treatment	Dose	Adjuvant		
	(µg)	AS01B (Number of subjects)	Water for injection (WFI) (Number of subjects)	
F4co (p24-RT-Nef-p17)	10	50	10	
F4co (p24-RT-Nef-p17)	30	50	10	
F4co (p24-RT-Nef-p17)	90	50	10	

[figure not shown]
[figure not shown]
[figure not shown]

Figure 1 Overall study design overview

(Amended September 24, 2007)

(Amended September 24, 2007)

Each vaccination in each dose group will be administered to the first 12 subjects at the rate of maximum 1 subject per day during the first 5 working days. After that period, provided stopping rules do not apply, the rate of vaccination will be unlimited.

* Holding rules = vaccinations will be put on hold if at least 3 out of the 12 subjects develop a Grade 3 general solicited AE, during the 7-day follow-up period after vaccination which persists at Grade 3 for more than 48 hours and which is considered to be related to vaccination **or** if at least 4 out of the 12 subjects develop any other Grade 3 unsolicited AE considered to be related to vaccination during the 7-day follow-up period after vaccination **or** if at least 4 out of the 12 subjects develop any Grade 3 general solicited (persisting at Grade 3 for more than 48 hours and considered related to vaccination) or unsolicited AE (considered related to vaccination) during the 7-day follow-up period after vaccination **or** at least one life threatening vaccine related SAE occurs **or** at least one subject shows ulceration (necrosis of the dermis) at the injection site following vaccination. The same approach will be repeated with each of the three vaccine doses (10, 30 and 90 µg) and for each of the three two vaccinations (see Section 5.6.3).(**Amended September 24, 2007**)

• Experimental design: Single center, dose-escalating, staggered, parallel-group study with 6 groups (Figure 1 and Figure 2):

3 groups of 50 subjects receiving the candidate vaccine F4co (p24-RT-Nef-p17), adjuvanted with AS01B, respectively at 10, 30 or 90 μg.

3 groups of 10 subjects receiving the candidate vaccine F4co (p24-RT-Nef-p17), non-adjuvanted, in water for injection, respectively at 10, 30 or 90 µg.

- Control groups: None.

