10.4. Estimated sample size

As this study is a first evaluation of safety and immunogenicity of the HIV candidate vaccine F4co, no formal sample size determination has been performed.

However, Table 11 presents the precision achieved for estimation of the primary parameters.

Table 11Precision achieved for different estimated proportions and for the
two sample sizes of 10 and 50 subjects [by PASS 2005, 95%
confidence interval of a proportion].

Estimated proportion	Precision N=50	Precision N=10
0.20 or 0.80	0.10	0.20
0.40 or 0.60	0.14	0.30

If we want to compare the three adjuvanted groups in terms of proportion of subjects with a given adverse event or in terms of proportion of responders to a vaccine antigen, the sample size of 50 subjects per group would achieve 80% power to detect around 20-30% difference in proportions with a two-sided alpha level of 0.0167 (Bonferroni's adjustment for 3 comparisons) (see Table 12).

Table 12Difference between 2 groups of 50 subjects that can be detected
with a power of 80% (two-sided alpha of 0.0167 for multiple
comparisons between three groups) (by PASS 2005, two
independent proportions, Fisher's Exact test)

Proportion in group 1	Proportion in group 2	Difference in proportions
0.10	0.38	0.28
0.20	0.52	0.32
0.30	0.63	0.33
0.40	0.73	0.33
0.50	0.82	0.32
0.60	0.89	0.29
0.70	0.95	0.25
0.80	0.99	0.19

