#### 3.3.5.2. Between group assessment

For the following analyses, statistically significant differences (p-value  $\leq 0.05$ ) should be interpreted with caution as adjustment for multiplicity of endpoints and clinical relevance of the difference will not considered.

| gsk
GlaxoSmithKline | Stu                | dy RAP           |
|------------------------|--------------------|------------------|
| Study Id: 108706       | Abbreviated Title: | PRO HIV-005      |
| Version: Draft version | 🗵 Final            | Date: 26SEP 2008 |

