### Analysis of frequency of CD4+ T-cells

A two-way ANOVA test will be performed on frequency of CD4+ T-cells expressing at least IL-2 to compare three doses of antigen F4Co with or without adjuvant two weeks after the second vaccination. The ANOVA model will include the doses (10  $\mu$ g, 30  $\mu$ g and 90  $\mu$ g) and the "adjuvants" (AS01B and WFI) as fixed effects.

If requires, the analysis will be performed on log10 frequency of CD4+ T-cells.

If interaction between doses and "adjuvant" is significant (p-value  $\leq 0.05$ ), comparison of doses will be done by "adjuvant" factor.

If difference between the three doses is significant (p-value  $\leq 0.05$ ), multiple comparisons will be performed and relationship between doses and CD4+ T-cell response will be also assessed.

ANOVA analyses will be done for each antigen (p17, p24, RT, Nef) and for the fusion protein F4Co.

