## Analysis of responders in terms of CD4+ T-cells

A logistic regression will be performed on occurrence of responders in terms of CD4+ Tcells expressing at least IL-2 (dichotomous response, 0 or 1) to compare three doses of antigen F4Co with or without adjuvant two weeks after the second vaccination. Doses, "adjuvant" and interaction will be included in the logistic model.

If interaction between doses and "adjuvant" is significant (p-value  $\leq 0.05$ ), a logistic regression will be applied by "adjuvant" factor.

Logisitic regressions will be done for responders to at least one, two, three and 4 antigens (p17, p24, RT or/and Nef).

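### For CD4+ T-cell frequency, dose contrasts and the dose-response assessment are planned only if the overall dose test has p ≤ 0.05; dose differences and a log-dose trend with 95% CIs should be reported whatever that p-value

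*SAP*

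**What the plan says.** SAP 3.3.5.2 describes two between-group analyses of the data from two weeks after the second vaccination.

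- **Frequency.** "A two-way ANOVA test will be performed on frequency of CD4+ T-cells expressing at least IL-2", with dose and adjuvant as fixed effects. If the dose-by-adjuvant interaction has p ≤ 0.05, "comparison of doses will be done by 'adjuvant' factor". The next step is conditional: "If difference between the three doses is significant" (p ≤ 0.05), "multiple comparisons will be performed and relationship between doses and CD4+ T-cell response will be also assessed". Nothing is specified for p > 0.05. The ANOVA is run five times: once for each of the four antigens and once for F4co.
- **Responders.** A logistic regression is fitted for response to at least one, two, three and all four antigens. "Doses, 'adjuvant' and interaction will be included in the logistic model". There is no condition on an overall dose p-value, but no pairwise dose difference or interval for one is named.

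The section's opening says that significant differences "should be interpreted with caution as adjustment for multiplicity of endpoints and clinical relevance of the difference will not considered". It gives no guidance on non-significant ones.

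Protocol 10.4 states that there was no formal sample size calculation, but it frames group size in pairwise terms: "If we want to compare the three adjuvanted groups in terms of proportion of subjects with a given adverse event", continuing to the proportion responding to an antigen. Table 12 lists differences between two groups of 50. SAP 3.4 makes every interval a two-sided 95% CI.

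**The concern.** The title calls this a dose-ranging study, so how the response changes across 10, 30 and 90 µg is a central comparative question. Under the frequency plan, the pairwise and dose-response analyses disappear when the overall test is non-significant. That is when an interval is most needed, to show how large a difference remains compatible with the data.

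The listed outputs do not fill the gap. Template Table I-3 gives mean, SD and quartiles by group, without intervals. Template Table I-2 gives responder percentages with an interval for each group, not for a difference. The list of tables in SAP 5.2 contains no between-dose table.

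**Working it through.** **1. The plan's own figure.** Protocol Table 12 claims 80% power for Fisher's exact test with 50 v 50 at two-sided alpha 0.0167. Exact power is the sum, over all pairs (x1, x2) with Fisher p ≤ 0.0167, of Bin(x1; 50, p1) × Bin(x2; 50, p2). For the eight rows in order this gives 0.786, 0.793, 0.803, 0.805, 0.806, 0.802, 0.800 and 0.788. The table reproduces. It covers proportions only; no power is stated for frequency.

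**2. Inputs.** From protocol section 3: 50 subjects per AS01B dose and 10 per WFI dose. From SAP 3.3.5.2: alpha 0.05. Assumed, because the documents give no SD or target difference: a largest dose difference of 0.5 within-group SD, normal data and everyone evaluable.

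**3. Overall F test within AS01B.** Noncentrality λ = n Σ(μi − μ̄)²/σ², with 2 and 147 df.

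- Means 0/0.25/0.5 SD: λ = 50 × 0.125 = 6.25; power 0.593; missed 40.7%.
- Means 0/0/0.5 or 0/0.5/0.5 SD: λ = 50 × 0.1667 = 8.33; power 0.727; missed 27.3%.

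At other ranges the miss rate is 48–59% (0.4 SD) and 12–24% (0.6 SD). With 45 evaluable per group it is 32–46% at 0.5 SD.

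**4. Additive two-way model, all 180, same dose effect in WFI.** There are 60 per dose and 180 − 4 = 176 error df.

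- 0/0.25/0.5: λ = 60 × 0.125 = 7.5; power 0.680; missed 32.0%.
- 0/0/0.5: λ = 60 × 0.1667 = 10; power 0.808; missed 19.2%.

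**5. The written sequence.** The plan reaches the AS01B-only test only after a significant interaction. That happens in about 5% of trials if the dose effect is common to both strata, and in 13–17% if it exists only in AS01B. Simulating interaction test then dose test (200,000 runs) gives these miss rates:

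| Dose test | Common effect | AS01B only |
|---|---|---|
| Type II | 20–32% | 32–45% |
| Type III | 45–57% | 70–77% |

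The SAP does not state the sum-of-squares type.

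**6. Is the condition the cause of low power?** For an unconditional pairwise t-test at n = 50, the noncentrality is 0.5/√(2/50) = 2.5 with 98 df. Power is 0.697 at alpha 0.05 (30% missed) and 0.528 at 0.0167 (47% missed). So the condition is not the main cause.

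**7. What the condition withholds.** The doses rise by a factor of 3 each time, so they are equally spaced on the log scale and the trend contrast is (−1, 0, 1). Its noncentrality is also 2.5, with 147 df, and its power is 0.700. For 0/0.25/0.5 SD the overall test that must be passed first has power 0.593. By simulation, when the overall test has p > 0.05 the trend is significant in 30% of those trials: 0.407 × 0.30 ≈ 0.12 of all trials. For 0/0/0.5 or 0/0.5/0.5 the overall test (0.727) is slightly stronger than the trend (0.700), so this argument is weaker there.

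**8. What an interval would show.** For a pairwise frequency difference the 95% half-width is 1.976 × √(2/50) = 0.40 SD. For responders it is 1.96 × √(2 × 0.16/50) = 16 points at 80% v 80%, and 1.96 × √((0.21 + 0.24)/50) = 19 points at 70% v 60%. Differences of that order can remain open after p > 0.05.

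**The case against.** The case for leaving the text alone has several parts.

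- An overall test before pairwise comparisons is a conventional protected procedure, and the SAP already runs five ANOVAs and four logistic models without adjustment across endpoints. This stands as a reason to treat added contrasts as descriptive. It does not explain why the dose-response estimate should also depend on the overall test.
- The ANOVA is supplementary: SAP section 4 lists the between-group assessment as an addition to the protocol. The primary immunogenicity objective concerns responder proportions, whose logistic model is not conditional on an overall dose test. This stands, and it confines the point about conditionality to frequency.
- Responder percentages with 95% CIs, and frequency means with SDs, are always tabulated by group, so a reader could build approximate unadjusted intervals. This also stands: the reader is not left with a p-value alone. But the plan should supply the contrast.
- The template tables are within-group tables, so their layout does not prove what the model output would omit. True. The gap is that nothing is specified.
- SAP 2.5 says that the Month 2 analysis, which covers Day 44, had been performed, and SAP 3.3.1 describes the Month 12 analyses as descriptive only. Any change is therefore a late addition and must be labelled so.

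A reader might also infer that the sponsor will treat p > 0.05 as showing equal doses. The documents do not say so; they are silent on how a non-significant result will be read.

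**Conclusion.** The point holds in a limited form. For CD4+ T-cell frequency, the plan makes dose contrasts and the dose-response assessment depend on an overall p ≤ 0.05 and provides no estimate otherwise. For responders there is no such condition, but no pairwise dose difference or interval is named, although protocol 10.4 discusses group size in those terms.

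A reader might take 27–41% as the plan's miss rate. It is not: it belongs to an AS01B-only overall test at an assumed 0.5 SD, and the corresponding range for the additive model on 180 is 19–32% with a shared effect. All these rates move with the assumed effect, the position of the third dose and the model. Nor do they measure harm done by the condition, since unconditional tests are also weak. Its cost is the missing estimate, including a significant log-dose trend left unassessed in about 12% of trials under 0/0.25/0.5 SD (AS01B-only calculation). This is a cheap improvement, not a flaw that invalidates the analysis.

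**What to change.** Replace the conditional sentence in SAP 3.3.5.2 so that the following are reported within AS01B whatever the overall dose p-value:

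- the three pairwise dose differences, for CD4+ frequency (as differences or ratios) and for responder proportions on each primary responder endpoint, with 95% CIs in line with SAP 3.4;
- a linear trend on log(dose) with its 95% CI.

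Bonferroni 98.33% CIs, matching protocol 10.4, may be added as a supplement. State that p > 0.05 on the overall test is not evidence that the doses are alike, and label the output as added after the Month 2 analysis.

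The cost is some SAP wording and an additional table from data already collected. The downside is that more unadjusted contrasts are shown, and they must be read as descriptive.

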## Analysis of responders in terms of CD4+ T-cells

A logistic regression will be performed on occurrence of responders in terms of CD4+ Tcells expressing at least IL-2 (dichotomous response, 0 or 1) to compare three doses of antigen F4Co with or without adjuvant two weeks after the second vaccination. Doses, "adjuvant" and interaction will be included in the logistic model.

If interaction between doses and "adjuvant" is significant (p-value  $\leq 0.05$ ), a logistic regression will be applied by "adjuvant" factor.

Logisitic regressions will be done for responders to at least one, two, three and 4 antigens (p17, p24, RT or/and Nef).

## 3.3.6. Humoral response

#### 3.3.6.1. Within group assessment

For humoral immune response, the following parameters will be tabulated by vaccine groups for each antigen (p17, p24, Nef, RT and F4co) at months 0, 2, 6, -7, 12 and at day 44 (two weeks after the second vaccination) :

- Geometric mean titers (GMTs) with 95% confidence intervals (CIs);
- Seropositivity rates with exact 95% CIs.

| gsk
GlaxoSmithKline | Stu                | dy RAP           |
|------------------------|--------------------|------------------|
| Study Id: 108706       | Abbreviated Title: | PRO HIV-005      |
| Version: Draft version | ⊠ Final            | Date: 26SEP 2008 |

## 3.4. Methodology for computing CI

All CI will be 2 sided 95% CI.

- The exact 95% CIs for a proportion within a group will be calculated from Proc StatXact [Clopper CJ, Pearson ES. The use of confidence or fiducial limits illustrated in the case of binomial. *Biometrika*. 1934;26:404-413].
- The 95% CI for geometric mean titers/concentrations (GMTs/GMCs) will be obtained within each group separately. The 95% CI for the mean of log-transformed titer/concentration will be first obtained assuming that log-transformed values were normally distributed with unknown variance. The 95% CI for the GMTs/GMCs will be then obtained by exponential-transformation of the 95% CI for the mean of log-transformed titer/concentration.

| gsk
GlaxoSmithKline | Stu                | Idy RAP          |  |
|------------------------|--------------------|------------------|--|
| Study Id: 108706       | Abbreviated Title: | PRO HIV-005      |  |
| Version: Draft version | i ⊠ Final          | Date: 26SEP 2008 |  |

## 4. CHANGE FROM PROTOCOL

The cut-off will be choosen on the basis of pre-vaccination response for all subjects, by examining percentiles (95th percentile included) of the different antigens and the different cytokines (amendment 1). A 95th percentile will be determined for each antigen on the CD4 expressing at least two cytokines (all doubles) for CD4 responses and on the CD8 expressing at least one cytokine for CD8 responses. The cut-off will be defined as the rounded (superior hundred) maximum 95th percentile among the 4 antigens (amendment 1).

To avoid a bias of analyses, cut-off will be determined for each antigens and eachcytokines before the start of immunogenicity analyses (i.e., at the time of the preanalysis meeting) on the basis of pre-vaccination blinded data (amendement 1).

In addition to analyses described in the protocol for CD4+ T-cells expressing IL-2 and another cytokine:

- percentage of responders to one, two, three and four antigens will be tabulated, with and without specification of antigens;
- a between assessment group will be performed (see section 3.3.5.2)

# Cytokines measured for CD8+ T-cells response have been reduced to TNF- $\alpha$ and/or IFN- $\gamma$ (amendment 1).

The stepwise nature of the final analysis implied the use of a different cohort (called month 12 cohort) for the time points Month 6 and month 12 to account for the elimination of subjects between month 2 and month 12. It was agreed to use this Month 12 cohort for the SAE description and for the descriptive immunogenciity analysis. For this last type of analysis (immunogenciity), to avoid any possible confusion, tables for these month 6 and month 12 time points will be separate as those presented for the month 2 analysis for all preceding tilme points.

| gsk
GlaxoSmithKline | :                | Study RAP        |  |  |
|------------------------|------------------|------------------|--|--|
| Study Id: 108706       | Abbreviated Titl | e: PRO HIV-005   |  |  |
| Version: Draft version | on 🛛 🖾 Final     | Date: 26SEP 2008 |  |  |

## 5. INDIVIDUAL LISTINGS AND TABLES

## 5.1. Individual listings

Appendix Table I.A - Elimination codes

Appendix Table I.B - Demography

Appendix Table I.Ci - Dates of birth, Informed consent, Vaccination and blood sampling, Contact

Appendix Table I.Cii - Reason for visit not done

Appendix Table I.D - General medical history

Appendix Table I.E - Study conclusion

Appendix Table I.I - Reason for non administration of vaccine

Appendix Table II.A - Solicited local symptoms

Appendix Table II.B - Solicited general symptoms

Appendix Table II.Ci - Unsolicited adverse events within 31 days post-vaccination

Appendix Table II.Cii - Unsolicited adverse events after 31 days post-vaccination

Appendix Table II.Di - Concomitant medication

Appendix Table II.Dii - Concomitant vaccination

Appendix Table III.A - Immunogenicity (antibody response)

Appendix Table III.B - Immunogenicity (Cell-mediated immune response)

Appendix Table IV.A - Haematology

Appendix Table IV.B - Biochemistry

| gsk
GlaxoSmithKline | Stu                | Study RAP        |  |  |
|------------------------|--------------------|------------------|--|--|
| Study Id: 108706       | Abbreviated Title: | PRO HIV-005      |  |  |
| Version: Draft version | on 🛛 Final         | Date: 26SEP 2008 |  |  |
|                        |                    |                  |  |  |

## 5.2. List of tables

The following table summarizes all tables that will be produced for the planned interim (x for first interim analysis, xx for second interim analysis) and final analyses (see previous sections for detazils of cohort/analysis and time points):

| Denomination  | Template table          | Total
vaccinated
cohort    | ATP cohort for
immunogenicity | Macro     |
|---|-------------------------|----------------------------------|----------------------------------|-----------|
| Parameter setting in stat batches   |                         | Elim = 9                         | Elim = 2                         |           |
| 1. Study cohorts and demography analysis  |                         |                                  |                                  |           |
| 1.1. Study cohorts  |                         |                                  |                                  |           |
| Table D - 1 Number of subjects enrolled into the study as well as the number excluded from ATP analyses with reasons for exclusion. | Template Table
D - 1 | Table D.0-1
(Elim = 0) |                                  | %ELIMLIST |
| Table D - 2 Number of subjects at each visit and
list of withdrawn subjects  | Template Table
D - 2 | Supplementary
Table D.9-2     |                                  | %DROPOUT  |
| Table D - 3 Number of subjects vaccinated,
completed and withdrawn with reason for
withdrawal                                 | Template Table
D - 3 | Table D.9-3                      |                                  | %DROP_SUM |
| Table D - 4 Minimum and maximum activity
dates   | Template Table
D - 4 | Working Table
D.9-4           |                                  | %DATE     |
| Table D - 5 Number and percentage of subjects
who received vaccine dose(s)   | Template Table
D - 5 | Table D.9-5                      |                                  | %EXPO     |
| Table D - 6 Deviations from specifications for
age and intervals between study visits  | Template Table
D - 6 | Supplementary
Table D.9-6     |                                  | %INT_VAL  |
| 1.2. Demographic characteristics  |                         |                                  |                                  |           |
| Table D – 7 Summary of demographic
characteristics   | Template Table
D - 7 | Table D.9-7                      | Table D.9-8b                     | %DEMOGRA  |

| gsk
GlaxoSmithKline                         | Study RAP  |                |                      |                                  |          |
|--|------------|----------------|----------------------|----------------------------------|----------|
| Study Id: 108706                               | Α          | bbreviated Tit | le: PRO H            | HIV-005                          |          |
| Version: Draft version                         | X          | Final          | Date:                | 26SEP 2008                       |          |
| CONFIDENTIAL                                   |            |                |                      |                                  |          |
| Denomination                                   |            |                | Total                |                                  |          |
|  |            | Template table | vaccinated
cohort | ATP cohort for
immunogenicity | Macro    |
| 2. Reactogenicity/safety analysis              |            |                |                      |                                  |          |
| 2.1. Compliance                                |            |                |                      |                                  |          |
| Table R - 1 Compliance in returning symp       | otom       | Template Table | Working Table        |                                  | %COMPLI  |
|  |            | R-1            | R.9-1                |                                  |          |
| Table R - 2 Compliance to data capture         |            | R - 2          | Table R.9-2          |                                  | %CAPTURE |
| 2.2. All symptoms                              |            | N 2            |                      |                                  |          |
| Table R – 3.1 Incidence and nature of          |            |                |                      |                                  |          |
| symptoms (solicited and unsolicited) repo      | rted       | Template Table |                      |                                  |          |
| during the 7 days (Days 0-6) follow-up pe      | riod       | R-3            | Table R.9-3.1        |                                  | %LOUGEN  |
| after each dose and overall                    |            |                |                      |                                  |          |
| Table R - 3.2 Incidence and nature of gr       | ade 3      |                |                      |                                  |          |
| symptoms (solicited and unsolicited) repo      | rted       | Template Table | Table P 0 2 2        |                                  |          |
| during the 7 days (Days 0-6) follow-up pe      | riod       | R - 3          |                      |                                  | %LOCGEN  |
| after each dose and overall                    |            |                |                      |                                  |          |
| Table R – 3.3 Incidence and nature of          |            |                |                      |                                  |          |
| symptoms (solicited and unsolicited) with      | l .        | Template Table | Supplementary        |                                  |          |
| causal relationship to vaccination, repor      | ted        | R - 3          | Table R 9-3 3        |                                  | %LOCGEN  |
| during the 7-day (Days 0-6) post-vaccinal      | ion        |                |                      |                                  |          |
| period following each dose and overall         |            |                |                      |                                  |          |
| Table R – 3.4 Incidence and nature of gr       | ade 3      |                |                      |                                  |          |
| symptoms (solicited and unsolicited) with      | )
4 - 1 | Template Table | Supplementary        |                                  |          |
| causal relationship to vaccination, repor      | ted        | R-3            | Table R.9-3.4        | %LOCGEN                          |          |
| during the 7-day (Days 0-6) post-vaccinat      | ion        |                |                      |                                  |          |
| 2.2. Solicited exemptome                       |            |                |                      |                                  |          |
| Z.S. Solicited symptoms                        |            |                |                      |                                  |          |
| symptoms reported during the 7-day (Day        | (c 0_6)    | Tomplato Tablo |                      |                                  |          |
| post-vaccination period following each do      | so and     |                | Table R.9-4          |                                  | %FREQ    |
| overall  | Se anu     | 11 - 4         |                      |                                  |          |
| Table R – 5 Incidence of solicited genera      |            |                |                      |                                  |          |
| symptoms reported during the 7-day (Day        | (s.0-6)    | Template Table |                      |                                  |          |
| post-vaccination period following each do      | se and     | R - 5          | Table R.9-5          |                                  | %FREQ    |
| overall  |            |                |                      |                                  |          |
| Table R – 6.1 Number of days with sympt        | oms        | Template Table |                      |                                  |          |
| during the solicited post-vaccination period   | d          | R-6            | Table R.9-6.1        |                                  | %SYMPDUR |
| Table R - 6.2 Number of days with grade        | 3          | Templete Tekle |                      |                                  |          |
| symptoms during the solicited post-vaccir      |            | Table R.9-6.2  |                      | %SYMPDUR                         |          |
| period   | K-0        |                |                      |                                  |          |
| Table R - 6.3 Number of days with relate       | d          | Template Table | Supplementary        |                                  |          |
| symptoms during the solicited post-vaccination |            | R - 6          | Table R 9-6 3        |                                  | %SYMPDUR |
| period   |            | ŇŬ             |                      |                                  |          |
| Table R – 6.4 Number of days with Relate       | ed         | Template Table | Supplementary        |                                  |          |
| grade 3 symptoms during the solicited po       | st-        | R-6            | Table R.9-6.4        |                                  | %SYMPDUR |
| vaccination period                             |            | T              |                      |                                  |          |
| Table $R - / Maximum temperature per de$       | ose,       | remplate Table | Table R.9-7          |                                  | %FREQ    |
| overall doses, overall subject (0.5° increm    | ients)     | K-/            |                      |                                  |          |

| gsk
GlaxoSmithKline   | Study RAP  |                          |                                 |                                  |         |
|--|--|--------------------------|---------------------------------|----------------------------------|---------|
| Study Id: 108706   | A  | bbreviated Tit           | ile: PRO H                      | HIV-005                          |         |
| Version: Draft version   | n 🗵  | Final                    | Date:                           | 26SEP 2008                       |         |
|  |  | CONFIDENTI               | AL                              |                                  |         |
| Denomination   |  | Template table           | Total
vaccinated
cohort   | ATP cohort for
immunogenicity | Macro   |
| 2.4. Unsolicited symptoms  |  |                          |                                 |                                  |         |
| Table R – 8.1 Percentage of subjects
the occurrence of unsolicited sympton
classified by MEDDRA Primary Syster
Class and Preferred Term, within the 3
(Days 0-29) post-vaccination period   | reporting
ns
n Organ
30-day               | Template Table
R - 8  | Table R.9-8.1                   |                                  | %UNSOL  |
| Table R – 8.2 Percentage of doses wi
unsolicited symptoms classified by ME
Primary System Organ Class and Pre-
Term, within the 30-day (Days 0-29) p
vaccination period   | ith
EDDRA
ferred
ost-                     | Template Table
R - 9  | Table R.9-8.2                   |                                  | %UNSOL  |
| Table R – 8.3 Global Summary of un
signs and symptoms reported within the
(Days 0-29) post-vaccination period  | solicited
ne 30-day                             | Template Table
R - 10 | Table R.9-8.3                   |                                  | %UNSOL  |
| Table R – 9.1 Percentage of subjects
the occurrence of grade 3 unsolicited
classified by MEDDRA Primary Syster
Class and Preferred Term, within the 3
(Days 0-29) post-vaccination period  | reporting
symptoms
n Organ
30-day         | Template Table
R - 8  | Table R.9-9.1                   |                                  | %UNSOL  |
| Table R – 9.2 Percentage of doses wi
3 unsolicited symptoms classified by M
Primary System Organ Class and Prei
Term, within the 30-day (Days 0-29) p
vaccination period  | ith grade
/IEDDRA
ferred
ost-      | Template Table
R - 9  | Table R.9-9.2                   |                                  | %UNSOL  |
| Table R – 9.3 Global Summary of gra
unsolicited signs and symptoms repor
the 30-day (Days 0-29) post-vaccination   | ade 3
ted within
on period                   | Template Table
R - 10 | Table R.9-9.3                   |                                  | %UNSOL  |
| Table R – 10.1 Percentage of subject
reporting the occurrence of unsolicited
symptoms classified by MEDDRA Prin
System Organ Class and Preferred Te
causal relationship to vaccination, w
30-day (Days 0-29) post-vaccination p | s
I
nary
erm with
ithin the
period  | Template Table
R - 8  | Supplementary
Table R.9-10.1 |                                  | %UNSOL  |
| Table R – 10.2 Percentage of doses we
unsolicited symptoms classified by ME
Primary System Organ Class and Prei
Term with causal relationship to vac
within the 30-day (Days 0-29) post-vac
period                              | vith
EDDRA
ferred
ccination,
ccination | Template Table
R - 9  | Supplementary
Table R.9-10.2 |                                  | %UNSOL  |
| Table R – 10.3 Global Summary of u
signs and symptoms reported with ca
relationship to vaccination, within the
(Days 0-29) post-vaccination period  | insolicited
usal
30-day               | Template Table
R - 10 | Supplementary
Table R.9-10.3 |                                  | %UNSOL  |
| 2.5. Serious adverse events
Table R – 11 Listing of SAEs reported
whole study period   | during the   | Template Table
R - 11 | Table R.9-11                    |                                  | %SAE    |
| Z.o. Haematology and biochemistry
Table R – 12.1 Distribution of haemato
biochemistry with respect to normal la
ranges  | blogy and
boratory                              | Template Table
R - 12 | Supplementary
Table R.9-12.1 |                                  | %LAB_RW |

| gsk
GlaxoSmithk  | line   | Study RAP              |                          |                                 |                                  |           |
|---|--|------------------------|--------------------------|---------------------------------|----------------------------------|-----------|
| Study Id: 1087  | 06   | Α                      | bbreviated Tit           | le: PRO H                       | HV-005                           |           |
| Version:  | Draft version  |                        | Final                    | Date:                           | 26SEP 2008                       |           |
|   |  |                        | CONFIDENTI               | ΔΙ                              |                                  |           |
| Denom   | nation   |                        | Template table           | Total
vaccinated
cohort   | ATP cohort for
immunogenicity | Macro     |
| Table R – 12.2 Change f
haematological and biocl
respect to normal ranges                                 | rom baseline in
nemical levels w                                      | i ith           | Template Table
R - 1  | Supplementary
Table R.9-12.2 |                                  |           |
| Table R – 13 Incidence of
medication during the 30
vaccination period by dos                              | f concomitant
-day (Days 0-29
se and overall                       | ) post-                | Template Table
R - 14 | Supplementary
Table R.9-13   |                                  | %CMED_INC |
| 3. Immunogenicity table   | es   |                        |                          |                                 |                                  |           |
| 3.1. CD4+/CD8+ T-cells  | response by IC   | CS                     |                          |                                 |                                  |           |
| Table I – 1a Frequency of
expressing cytokines (by
vaccination: percentiles (                             | f CD4+ T-cells
ICS) at pre-
amendment 1)                           |                        | Template Table
I - 1  |                                 | Working Table
I.2-1a          | Specific  |
| Table I – 2 CD4+ T cells
cytokines including IL-2 :
percentage of responder
three and all 4 antigens   | expressing at le
Number and
s to at least one                      | east 2
e, two,      | Template Table
I - 2  |                                 | Table I.2-2                      | Specific  |
| 3.1.2. Secondary object   | ives   |                        |                          |                                 |                                  |           |
| Table I – 3 CD4+ T cells
cytokines including IL-2 :  | expressing at le
Descriptive stat                                     | east 2
tistics      | Template Table
I - 3  |                                 | Table I.2-3                      | %CMI      |
| Table I – 4 CD4+ T cells
cytokines including IL-2 :
percentage of responder                               | expressing at le
Number and
s per antigen                          | east 2                 | Template Table
I - 4  |                                 | Table I.2-4                      | specific  |
| Table I – 5 CD4+ T cells
cytokines including IL-2 :
percentage of responder
four antigens              | expressing at le
Number and
s to one, two, th                      | east 2
iree or      | Template Table
I - 5  |                                 | Table I.2-5                      | specific  |
| Table I – 6 CD4+ T cells
cytokines including IL-2 :
percentage of responder
four antigens with specifi | expressing at le
Number and
s to one, two, th
cation of antiger | east 2
ree or
ns | Template Table
I - 6  |                                 | Supplementary
Table I.2-6     | specific  |
| Table I – 7 CD4+ T cells
cytokines including TNF-  | expressing at le
α : Descriptive s                                    | east 2
statistics   | Template Table
I - 3  |                                 | Supplementary
Table I.2-7     | %CMI      |
